1.1.1 Inclusion Criteria

- Subject's signed and dated informed consent
- Patients between 5 and 16 years of age, but diameter of bone marrow canal at least 2 mm
- Alert person oriented to place and time
- Acute, radius and/or ulna shaft fractures (antebrachium diaphysis)

Clinical Investigation Plan

Bioabsorbable Intramedullary Nail Fixation of Forearm Fractures in Children

- Satisfactory alignment must be in prior considered to be achieved by closed or open reduction

1.1.2 Exclusion Criteria

- Previous fracture or infection of the injured forearm bones (i.e. the radius and/or ulna)
- Severe overweight; body mass index (BMI) over 30
- Fracture older than 5 7 days
- Distal fracture patterns in the transition zone of the distal metaphysis to diaphysis of the radius, classified as metaphyseal or metadiaphyseal fractures.
- Monteggia fracture dislocation
- Galeazzi fracture dislocation
- Open fracture other than a slight inside-out –wound and significant associated soft-tissue injury, particularly in connection with intra-articular fractures and polytrauma
- Pathological fractures with juvenile bone cysts
- Documented active infection at any anatomical site
- A known metabolic skeletal disease (such as osteoporosis or osteomalacia) or medication affecting the bone structure (cortisone treatment)
- Any underlying systemic illness (such as unbalanced diabetes mellitus or rheumatic disease) or condition which are known to affect resistance to infection
- Any other condition that in the judgment of the investigator would prohibit the subject from participating in the study or may hinder the collection of data and interpretation of the results.
- The patient has participated in any other device or drug related clinical trial within the previous month
- Patients certainly requiring open reduction to achieve satisfactory alignment

1.1.3 Number of Subjects

35 subjects will be treated under this protocol. At least 13 subjects are enrolled and treated in both groups to assess the safety and efficacy of the new implant. As there may occur

Clinical Investigation Plan

Bioabsorbable Intramedullary Nail Fixation of Forearm Fractures in Children

withdrawals there are more subjects to be treated than is required by samples size calculation.

Each study centre will operate at most two forearm fracture patients using the bioabsorbable intramedullary nails before the actual study subjects. This way the investigators will familiarize sufficiently with the surgical technique and use of bioabsorbable intramedullary nails in order that the outcome of the bioabsorbable intramedullary nails and titanium elastic nails would be comparable. These patients must be selected according to the chapter 9.2, and they and/or guardian must provide informed consent. The operations and the follow-up of their recovering will be performed according to this clinical investigation plan; however, according to a decision of the study group, these patients will not be included in the evaluation of the outcome and key variables.

1.1.4 Screen Failures

Subjects who sign an informed consent form and fail to meet the inclusion and/or exclusion criteria are defined as screen failures. For all screen failures, the investigator is to maintain a screening log that documents the screening number, subject initials, and the reason for screen failure.

Prior Treatment

Prior to treatment the subjects will sign an informed consent form, stating that they are acquainted with the surgical procedure and study, and that they consent to participate in the study.

Reasonable efforts will be made to determine all relevant treatment received by the subject within 4 weeks prior to administration of the randomized treatment assignment. All relevant information will be recorded on the subject's CRF:

- Patient demographics
- Aetiology (e.g. bicycle accident, fall, sports) and injury mechanism
- Fracture type
 - proximal, middle, or distal shaft according to anatomic location
 - angular and rotational deformities, and displacement

Concomitant Treatment

1.1.5 Permitted Treatment

The following concomitant medications and therapies will be permitted:

- The treatment normally clinically applied when fixation is carried out using TEN nails is acceptable also in this study. In other words, the patients will receive all treatments needed for their injuries as the standard of care defines. The concomitant medications, therapies and treatments, which may reasonably be expected to interfere with the results of forearm fracture healing, will be reported in CRF.
- Due to the nature of the study, it is acceptable to leave out the detailed dosage information of concomitant medication in the CRF. This means that “N.A.” (= not applicable/available) can be documented into the Concomitant Medication CRF into the columns of “Single dose and unit” and “Frequency”.

1.1.6 Prohibited Treatment

- Subjects will not be permitted to use other investigational treatments during the 12 months following administration of the randomized treatment assignment.
- To avoid potential interactions that may interfere with fracture healing, the following concomitant medications and therapies are prohibited:
 - Osteoporosis medications (such as bisphosphonates and SERMs)
 - Hormone replacement and calcium-D-vitamin preparations are, however, permitted
- Additional procedures for the region of the study which may interfere fracture healing (such as ultrasound treatment)

Assessments and Procedures

1.1.7 Visit Schedule

For each subject, the study consists of assessments preoperatively, immediately after operation and the follow up visits postoperatively. The recommend time window of scheduled visits is ± 7 days. The clinical assessments and procedures performed at each visit are shown in Table 2.

Clinical Investigation Plan

Bioabsorbable Intramedullary Nail Fixation of Forearm Fractures in Children

During these visits will be investigated: function of both arms, radiological fracture healing, well-being and incidence of complications.

Table 2 Assessment and procedures at each visit

Assessment	Operation		4 week	12 weeks	26 weeks	52 weeks	104 weeks
	Pre-operative	Post-operative					
	Visit 1	Visit 2	Visit 3	Visit 4	Visit 5	Call 6	Visit 7
Informed consent, inclusion and exclusion criteria	X						
Demographics, medical history	X						
Injuries and comorbidities	X						
Randomization	X						
Fracture reduction and fixation	X						
Cast removal			X				
TEN nail removal					X		
Primary performance variable	Operation		4 week	12 weeks	26 weeks	52 weeks	104 weeks
	Pre-operative	Post-operative					
	Visit 1	Visit 2	Visit 3	Visit 4	Visit 5	Call 6	Visit 7
Functional and clinical outcome evaluated by measuring rate of motion			X	X	X		X
Pain assessment		X	X	X	X	X	X
Subjective		X	X	X	X	X	X

Clinical Investigation Plan

Bioabsorbable Intramedullary Nail Fixation of Forearm Fractures in Children

result							
Secondary variables	Operation		4 week	12 weeks	26 weeks	52 weeks	104 weeks
	Pre-operative	Post-operative					
	Visit 1	Visit 2	Visit 3	Visit 4	Visit 5	Call 6	Visit 7
Radiographic outcome and bone union formation evaluated by plain radiographs	X	X	X	X	X		X
Radiographic outcome and bone union formation evaluated by MRI imaging		X*		X*		X*	X*
Safety and tolerability variables	Operation		4 week	12 weeks	26 weeks	52 weeks	104 weeks
	Pre-operative	Post-operative					
	Visit 1	Visit 2	Visit 3	Visit 4	Visit 5	Call 6	Visit 7
Adverse events	X	X	X	X	X	X	X
Concomitant medications	X	X	X	X	X	X	X
Conclusion of participation							X

* Radiographic outcome and bone union formation of 5-10 subjects will be evaluated by MRI imaging immediately after operation and three follow up visits

1.1.8 Surgical Procedure

The surgery will be performed by a paediatric surgeon, paediatric orthopaedic surgeon, orthopaedic surgeon or by a resident specializing in paediatric orthopaedic surgery. In surgery, standard AO techniques will be applied. The surgery will have the following steps:

1. Patients are placed supine on a standard operating room table and general anesthesia is induced.
2. The arm is prepared and draped in the usual sterile fashion. A tourniquet is used as necessary, according to the decision of the operating surgeon.

Clinical Investigation Plan

Bioabsorbable Intramedullary Nail Fixation of Forearm Fractures in Children

3. Following necessary irrigation of any open wounds, attention is then turned to IM nailing.
 - a. The more angulated/displaced bone is addressed first and stabilized.
 - b. If the second bone reduces anatomically with stabilization of the first bone, it is treated closed
4. Either a bone awl or a 4.5-mm drill bit is used to make an entry portal into the cortical bone
 - a. To treat the radius, a 1-cm longitudinal incision is made over the dorsolateral metaphyseal surface just proximal to distal physis (C-arm image is used to aid in the placement of the incision), with care taken to avoid the dorsal branch of the superficial radial nerve.
 - b. All ulnae are treated by inserting the IM device from proximal to distal, avoiding the proximal physis using the above technique.
5. If an acceptable reduction cannot be achieved closed, then a mini open incision directly over the fracture site is made and any interposing tissue removed.
6. Bone marrow canal is reamed using the metallic intramedullary nail (\varnothing 2.0, 2.5, 3.0 or 3.5 mm).
 - a. The reaming metallic intramedullary nails are left to bone marrow canals until it is time to insert bioabsorbable IM nail. The metallic intramedullary nails are removed and replaced by bioabsorbable IM nail one by one.
 - b. The diameter of the metallic intramedullary nail and bioabsorbable IM nail will be determined according to the estimation about the diameter of bone marrow canal by radiograph. The largest possible implant is to be applied.
7. After reaming of canal, the bioabsorbable IM nail (\varnothing 2.0, 2.7 or 3.2 mm) is inserted to canal using nail inserter.
 - a. In the installation of bioabsorbable IM nail the “slide hammer” of the insertion tool has to be used without rotational motion, because the nail may expand because of heat due to rotational motion and friction.
 - b. Use of drill sleeve is recommended during installation of the nail.
8. Following insertion of the bioabsorbable IM nail, it is cut using oscillating saw or hot wire.
9. The wounds are closed in layers using standard principles.
10. The immobilization of forearm is performed by dorsal plaster cast with volar support for 4 - 6 weeks with the elbow flexed to 90 degrees. After that, additional appropriate immobilization should be considered by the treating physician.
11. Sport activities should be limited for 3-6 months.

Clinical Investigation Plan

Bioabsorbable Intramedullary Nail Fixation of Forearm Fractures in Children

The operation technique is much the same as that with metallic IM nailing fixation. The differences of techniques are that

- the separate reaming of bone marrow is not performed with metallic IM nail fixation
- the end of the TEN nail is left out about 6 - 7 mm from the cortex for removing of the nail
 - Wound is closed in layers over the end of the TEN nail
- the TEN nail is removed in second operation after 6 months in general anesthesia.

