- [name], Chief Paediatric Radiologist

Central Hospital of Päijät-Häme, Department of Surgery

[name]

- [name], PhD, Orthopaedic Surgeon

Clinical Investigation Plan

Bioabsorbable Intramedullary Nail Fixation of Forearm Fractures in Children

Synopsis

Name of Sponsor: Bioretec Ltd.
Name of Medical Device: Bioabsorbable Intramedullary Nail
Title of Study: Bioabsorbable Intramedullary Nail Fixation of Forearm Fractures in Children
Investigators: 
○ [name], PhD, Associate Professor, Paediatric Surgeon○ [name], PhD, Orthopaedic Surgeon○ [name], Statistician○ [name], MB, PhD candidate○ [name], Paediatric Radiologist○ [name], Professor, MD, PhD, Paediatric Orthopedist and Surgeon○ [name], [name], PhD, Paediatric Orthopedist and Surgeon
Study Centres: 
- Oulu University Hospital, Department of Children and Adolescents- Central Hospital of Päijät-Häme, Department of Surgery, Unit of Paediatric Surgery
Studied Period (weeks): 52 (follow up 2 years) Date of First Enrolment: 2010 Date of Last Completed: 2018
Objectives: 
Primary objective: Clinical outcome of the fracture treatment is equal between patients treated by the new bioabsorbable medical device and by standard of care using a titanium alloy device. This will be assessed by functional and clinical outcome measuring range of motion of forearm, wrist and elbow and pain assessment at two-years' follow-up.
 
Secondary objective: The new medical device (bioabsorbable intramedullary nail) is at least as good as the routinely used device (elastic stable titanium alloy intramedullary nail) in forearm fracture treatment to achieve a level of reduction and stabilisation that is appropriate to the age of the child. This will be assessed by radiological outcome and determination of bony union formation and alignment in the healing forearm fracture using radiographic methods; further, soft-tissue and bone-tissue reactions are to be evaluated by MRI.

Methodology:

Clinical Investigation Plan

Bioabsorbable Intramedullary Nail Fixation of Forearm Fractures in Children

The fracture is fixed using the new medical device (bioabsorbable intramedullary nail) or the standard titanium intramedullary nail.

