Bioretec's ActivaPin™ products have gained excellent clinical outcome in the different indications of orthopedics and trauma surgery. The modified (lengthened) bioabsorbable devices for fixation of children's unstable forearm fractures are manufactured by Bioretec Ltd based on ActivaPin™ technology. Devices are intended for repair of children's unstable forearm (radius and/or ulna) fractures. In addition to extended length an X-ray marker has been added to the tip of the implant to facilitate the similar insertion technique applied for TEN nails, which utilizes fluoroscopy to monitor the position of the tip of the implant intra-operatively. The main purpose of the device is to stabilize diaphyseal forearm fractures of children in the alignment of the repositioned state for at least 6 weeks in the presence of appropriate immobilization and to obviate the need for second operation to remove the hardware. The operation technique of these bioabsorbable IM nails is very similar to that of metallic IM nails.

Preclinical Testing

Preclinical testing is not applied, as the materials have known toxicological profiles and well-established track record of safe clinical use in other application areas comparable to intramedullary nail fixation of forearm fractures. The manufacturing methods of bioabsorbable IM nails are well established in manufacturing of similar implants to different application areas.

Risk Analysis and Risk Assessment

The risk management of this clinical investigation has been made according to current risk management standard for medical devices (ISO 14971) and according to risk assessment the residual risk is acceptable. Based on risk assessment the risk is negligible that the 85/15 PLGA implants would cause any bioincompatibility reactions in this indication. The residual risk of each hazard was estimated based on the probability and severity of occurrence.

Objectives

Primary Objectives

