1.1.9 Functional and Clinical Outcome Measurements

Healing of the injury will be clinically monitored using repeated functional measurements, pain assessments and by means of standardized questionnaires. The follow-up will be performed according to table 2. The functional examinations will include the supination and pronation of the forearm, flexion and extension of elbow, dorsiflexion and palmar flexion of the wrist using a goniometer, and their comparison to the corresponding measurements of the subject's healthy forearm.

[figure not shown]

Figure 1 Determination of forearm's pronation and supination angles

In measuring of pronation, the vertical limb of the goniometer is placed parallel to the long axis of the humerus, while the horizontal limb is placed on the back of the wrist (to eliminate additional motion at the radiocarpal joint). In the measuring supination the horizontal limb is placed on the anterior aspect. The average range of pronation/supination is 90/90 degrees (50/50 degrees necessary for activities of daily living). ***Flynn's criteria for elbow assessment is used to evaluate the clinical significance of outcomes (excellent and good comprising satisfactory, and fair and poor comprising unsatisfactory), as well as the classification by Price.***

[figure not shown]

Figure 2 Determination of A) elbow's flexion and extension, B) wrist's dorsiflexion and palmar flexion

Clinical outcome and fracture union will be also assessed by the absence of pain and bony tenderness at fracture site. The subjects will be also asked to perform self-assessment of perceived pain in the region of study using 10 cm visual analogue scale (VAS) as a measure of pain severity.

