1.1.14 Other Variables

Other variables documented in CRF are:

- Operation time
- Number of days lost from usual activities
 - Parents lost working days
- Length of hospitalization stay
- Complaints in daily living
- Esthetics

Statistics

Recommended statistical methods will be applied. All deviations made after approval of the CIP will be described and justified in the final study report.

Sample Size Considerations

Primary outcome variable in this study is loss of supination and pronation within 6, 12, 26, 52, and 104 weeks after surgery. The non-inferiority margin is set to be 80 % in the calculations (=Power).

It is previously known that the forearm pronation in this age group is 81.2 degrees (95% CI 79.6-82.28) and 79.6 degrees (95% CI 78.8-80.4) in girls and boys, respectively. The corresponding supination archs are 90.0 degrees (95% CI 88.0-92.0) and 87.8 degrees (95% CI 85.7-89.9). [26] The standard deviation (SD) is 6.1 degrees in pronation and 7.6 degrees in supination. We determined that the new method (ActivaNail –intramedullary fixation) should

Clinical Investigation Plan

Bioabsorbable Intramedullary Nail Fixation of Forearm Fractures in Children

result to the forearm rotational range of motion that is not more than 15 degrees lower, compared to the rotational range of motion in TEN group, according to the Price's classification (<15 degrees of decrease refers to excellent outcome).

Difference between means in the groups is set as 7.0 and the Alpha as 0.05. The sample size is estimated to be 13 experimental subjects and 13 controls according to an unpaired two sample Student t test. This study population will also be exclusively large enough to recognize decrease in the ROM that is clinically significant (>15 degrees of decrease in supination or pronation in ActivaNail compared to TEN group).

Statistical Hypothesis

The following hypothesis will be tested for the primary efficacy variable:

H₀: Investigational device is inferior to comparative devices

H₁: Investigational device is non-inferior to comparative devices

The non-inferiority limit is set to 80 %. Thus, non-inferiority is shown if the upper limit of the 95% confidence interval for the difference is less than or equal to 5 %.

Statistical Methods

All operated subjects who reach the 2-year follow-up will be included in the statistical analysis. Study data will be tabulated by treatment groups with descriptive summary statistics.

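### Cast duration, the cast-removal visit and the motion time points do not agree, and the primary repeated-measures analysis does not say whether week-4 motion counts

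*Protocol*

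**What the plan says.** All references are to the protocol.

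- **Cast duration.** Section 1.1.8, step 10: a "dorsal plaster cast with volar support for 4 - 6 weeks with the elbow flexed to 90 degrees". The next sentence reads "After that, additional appropriate immobilization should be considered by the treating physician".
- **Cast removal.** Table 2 (section 1.1.7) has one mark for cast removal, at the 4-week visit (Visit 3).
- **Motion visits.** Under the primary performance variable, Table 2 lists "Functional and clinical outcome evaluated by measuring rate of motion" at 4, 12, 26 and 104 weeks. The 52-week contact is a call without a motion measurement.
- **Window.** "The recommend time window of scheduled visits is ± 7 days".
- **What is measured.** Section 1.1.9: "supination and pronation of the forearm, flexion and extension of elbow, dorsiflexion and palmar flexion of the wrist using a goniometer", with follow-up according to Table 2.
- **Primary time points.** Sample Size Considerations: "Primary outcome variable in this study is loss of supination and pronation within 6, 12, 26, 52, and 104 weeks after surgery".
- **Primary objective.** The synopsis assesses it by "measuring range of motion of forearm, wrist and elbow and pain assessment at two-years' follow-up".
- **Analysis.** Statistical Methods prescribes an analysis of variance for repeated measurements of the primary variable, without naming visits. The analysis covers operated subjects who reach the 2-year follow-up.
- **Blinding.** Type and Design of the Study states that the trial cannot be blinded.

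**The concern.** Forearm rotation, elbow motion and wrist motion cannot be validly measured in a plaster cast that holds the elbow at a right angle. The surgical section allows the cast to be on at a visit where Table 2 expects it off and the primary variable measured. Some week-4 values may therefore be missing, and others may mainly reflect how recently the cast came off.

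This matters for the treatment comparison only if week 4 contributes to it. The protocol leaves that open, because it gives three different descriptions of when the primary outcome is assessed. If week 4 does contribute, an effect of cast timing could be read as an effect of the implant. Cast time within the permitted range is decided by clinicians who know the implant, and no criterion or common rule for the two arms is given.

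**Working it through.** **1. Cast against visit window.** Visit 3 is planned at week 4, plus or minus 1 week, so it falls in weeks 3 to 5. The cast is to come off in weeks 4 to 6.

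- Overlap: weeks 4 to 5. A cast removed then can come off at an in-window Visit 3.
- Cast on for more than 5 and up to 6 weeks: it cannot be off at any in-window Visit 3. The next scheduled motion measurement is at week 12.
- Visit 3 held between weeks 3 and 4: removing the cast at that visit would fall short of the 4-week minimum in section 1.1.8.
- Cast removed in weeks 4 to 5 but after the child's own Visit 3: no valid motion value at that visit either.

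**2. Motion time points side by side.**

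- Table 2: 4, 12, 26, 104 weeks.
- Sample Size Considerations: 6, 12, 26, 52, 104 weeks.
- Synopsis, primary objective: two years, that is, 104 weeks.
- In both lists: 12, 26, 104. Only in Table 2: 4. Only in Sample Size Considerations: 6 and 52.

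Only 104 weeks is common to all three. Table 2 has no 6-week visit, so the 6-week motion value cannot be collected as scheduled. If week 6 was the intended first time point, a child in a cast until week 6 would be measured just as it came off.

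**3. How far week 4 could move the treatment effect.** The documents give no figure for the effect of recent casting on motion, or for any difference in casting between arms. Both are assumed here, with a range. Let *g* be the difference between arms in the proportion cast late, and *d* the change in measured week-4 rotation that late casting causes.

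- Shift in the week-4 arm difference = *g* × *d*.
- Low end: 0.10 × 10 degrees = 1 degree. High end: 0.50 × 40 degrees = 20 degrees.
- If the treatment effect is an equal average over Table 2's four motion visits, the shift is a quarter of this: 1/4 = 0.25 degrees to 20/4 = 5 degrees.
- The planning difference in Sample Size Considerations is 7.0 degrees.
- On a 104-week contrast alone, the shift is about nil.

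This is a sensitivity range and not an estimate. Equal averaging is also an assumption, since the protocol does not state it.

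**4. The plan's own sample size.** A two-sided two-sample t test with a difference of 7.0, SD 6.1 and alpha 0.05 needs 12.96, so 13 per group, with power 80.1%. The stated figure of 13 is reproduced and is not in dispute here. With the stated supination SD of 7.6, power at 13 per group is 61.5%.

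**The case against.** **Four weeks lies within 4 to 6 weeks, and the window stretches to week 5.** This stands in part. The sections are compatible for casts removed in weeks 4 to 5. The conflict applies to casts kept on past Visit 3, and without exception to those past week 5. The protocol permits these and does not say what happens to the motion measurement.

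**Week 4 may not be a primary time point.** This is the strongest objection, and it limits the harm. Sample Size Considerations omits week 4 and the synopsis looks at two years. But Table 2 lists week-4 motion under the primary performance variable, section 1.1.9 follows Table 2, and the analysis excludes no visit. Inclusion is possible but not established.

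**Casting need not differ by arm.** This is fair. Section 1.1.8 lists the differences in technique between the two nails, and casting is not among them. A reader might infer differential casting from the lack of blinding, but the documents show only that it could happen. A reader might also take the device's purpose of holding the fracture "in the alignment of the repositioned state for at least 6 weeks in the presence of appropriate immobilization" as a sign of longer casts in the test arm. That sentence says how long the device should hold alignment and sets no cast duration.

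**A fall in power might be inferred.** For example, if 30% of children were still in a cast at week 4 and were dropped, 13 × 0.7 = 9.1, so about 9 per arm would remain, and power for 7.0 degrees at SD 6.1 would be 62.8%. The documents do not support this:

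- The 30% has no source.
- Dropping children for one missed early visit is not stated. The analysis set is defined by reaching two years, and handling of missing visits may be left to a statistical analysis plan that is not at hand.
- Thirteen is the minimum per group, while 35 are to be enrolled.
- The calculation tests for a difference, whereas the stated hypothesis is non-inferiority. Against the 15-degree limit described in Sample Size Considerations, with no true difference and a two-sided 95% interval, 9 per arm would give about 99.8% power at SD 6.1 and 97.5% at SD 7.6. The protocol's margin wording is itself unclear, so these figures only show how far the answer depends on the hypothesis chosen.

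**Conclusion.** The inconsistency is established from the text. Sections 1.1.7 and 1.1.8 agree only for casts removed in weeks 4 to 5, and the motion time points differ between Table 2, Sample Size Considerations and the synopsis. A child whose cast stays on past Visit 3 has no valid motion value until week 12.

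The effect on the primary result is conditional. It requires that week 4 enters the treatment effect and, for bias, that cast timing differs by arm. Under the assumed ranges and equal weighting of four visits, the bias would be 0.25 to 5 degrees against a planning difference of 7.0. It would be about nil if the contrast is taken at 104 weeks. No loss of power can be stated. The point is moderate in weight but cheap to settle.

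**What to change.** 1. Reconcile sections 1.1.7 (Table 2), 1.1.8 and Sample Size Considerations on the timing of cast removal and on the motion time points. This review takes no view on the cast duration.
2. Make sure the actual date of cast removal is recorded. The case report form is an appendix that is not shown, so it may already ask for it.
3. In Statistical Methods, define the primary contrast as the treatment difference in motion at 104 weeks, estimated from the repeated-measures model. This agrees with the synopsis.
4. Report week-4 motion descriptively only, and keep it out of the primary contrast.

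The cost is wording in a few sections and, if it is not yet collected, one date on the case report form. The downside is that the primary contrast gives up some information on early recovery, which would still be visible in the descriptive results.
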